5.1 Obtaining Informed Consent

5.1.1 Patient consent

Study staff will ensure that potential participants are aware that the study is separate from clinical care, and that declining to participate will have no effect on medical services.

Eligible individuals will be asked if they would like to participate in the study after research staff have read each section of the consent form to them, or allowed them to review the entire consent form, and answered any questions potential participants may have about the study. If the patient is willing to participate, they will provide written informed consent (i.e. an e-signature) on an iPad. Participants will have the opportunity to keep a copy of the consent sheet.

Following randomization to an audio-recording of their visit, patient participants will be consented to these activities in the same fashion detailed above.

If a participant is randomized to an in-depth interview, they will be consented on the day of their interview before the interview begins. [name], a member of the study team, or another study staff member will conduct the interview consents. [name] has been approved by leadership in the Duval County Health Department to consent participants for the interviews she will be conducting. Since these interviews will primarily be conducted remotely, we will be conducting verbal consents for the in-depth interviews.

Details on participant payment can be found in Section 6.

5.1.2 Provider / counselor consent

Informed consent will be obtained from providers and counselors to audio record their counseling sessions. Study staff will emphasize that enrollment is entirely voluntary and will not affect professional standing. If the provider/counselor is willing to participate, they will provide written informed consent (i.e. an e-signature) on an iPad.

5.1.3 Avoiding Coercion and Undue Influence

It is extremely important that participants do not feel coerced or subjected to undue influence to participate in this study. Research staff will strive to find a balance between being inviting towards participants, and respecting individual autonomy and each individual's right to decline.

5.1.4 Confidentiality

The confidentiality of research participants is critical to this study and will be respected at all times. Due to the sensitive nature of the topic of research, and because a breach of information could potentially harm study participants, study staff will make it clear from the start that patients' names will not be connected to any surveys, interviews, or audio-recordings, and that private information will be accessible only by study staff. Information pertaining to their clinical records will only be accessible to DOH staff, and will be stored in a separate secure dataset. We will collect first names, phone numbers, email addresses, and

addresses only, in order to be able to communicate via text and mail gift certificates to participants. We will give participants the option of using a pseudonym.

Recruitment staff will not ask any personally identifiable information from participants except for first name, phone number, email address, address for mailing gift certificates and contact information for up to two personal contacts, in case study staff can't reach the participant. During the recruitment process this means that study staff will not ask for a participant's date of birth, or ask potential participants to sign any forms prior to completing the informed consent process.

This study has been issued a Certificate of Confidentiality from the NIH to protect identifiable information from disclosure. This will allow the investigator and others who have access to research records to refuse to disclose identifying information on research participants in any civil, criminal, administrative, legislative, or other proceeding, whether at the federal, state or local level. There is a clause in each consent form describing the Certificate to patient participants.

**If there is any breach of PHI either by the loss of documents or the audio recorders, the research coordinator and PI will be notified immediately so they can immediately contact the FDOH IRB.

6. PARTICIPANT PAYMENTS

6.1 Patient participant payments

Patient participants will receive a \$20 gift certificate to a grocery store (called a gThankYou) when they enroll and complete the baseline survey post-visit. They will also receive a \$10 gift certificate upon completion of a follow-up survey at 3 months post enrollment by phone or email. The research staff will distribute and track all gift certificate disbursements in the database along with the date.

Additional compensation will be given to eligible patient participants who complete an in-depth qualitative interview (\$40) and/or have their visit audio-recorded (\$20).

Compensation will be given after clinic visits or interviews to improve retention throughout the visit when the majority of data collection occurs.

6.2 Provider /counselor participant appreciation

Due to Florida DoH policy, DoH staff are not able to accept gift cards or certificates. However, at staff meetings throughout the year, the study team will bring food to show appreciation to clinic providers and counselors.

7. DATA COLLECTION AND ANALYSIS

7.1 Outcomes of Interest

The primary outcome will be PrEP initiation within 3 months of the initial visit, as measured by PrEP prescriptions ascertained from chart review. Secondary outcomes include self-report of PrEP use at 3 months, as well as perceived HIV risk, knowledge of and interest in PrEP, decisional conflict, and interpersonal quality of HIV prevention care.

7.1.1 *Primary outcome*

- **PrEP prescriptions:** The number of participants who received a PrEP prescription and date of prescription, obtained by chart extraction from the medical record.

7.1.2 *Secondary outcomes*

- **Number of Patients Reporting PrEP use:** Participants will be contacted at follow-up and asked if took PrEP in the past 3 months regardless of where it was obtained.
- **Patient-Perceived HIV risk:** Participants will be asked about how worried they are about getting HIV in the next 6 months.
- **Knowledge of PrEP:** Participants will be asked a series of questions about PrEP to assess PrEP knowledge.
- **Decisional Conflict:** Participants will be asked questions derived from the Decisional Conflict Scale to provide a measure of decision quality about their HIV prevention decision immediately following their visit.
- **Interpersonal Quality of HIV Prevention Care:** A scale for patient-centered HIV prevention counseling focusing on patient preferences and reflecting satisfaction and confidence in the counseling session, derived from the Interpersonal Quality of Family Planning Care Scale developed by the PI.
- **Intention to Use Any HIV Prevention Method:** Participants will be asked if they plan to use any HIV prevention method after the initial visit.
- **Satisfaction with Information Received about HIV Prevention:** Participants will be asked about their satisfaction with HIV prevention counseling.
- **Perceived Quality of Information Received about HIV Prevention:** Participants will also be asked questions about the perceived quality of the HIV prevention information they received during their health care visit.
- **Acceptability of HIV Prevention Methods:** Participants will be asked to rate their preference for a method (even if they never used it). Participants can select from condoms, PrEP, PEP, treatment as prevention, regular partner testing, or other method.
- **Acceptability of the Decision Support Tool:** Participants in the experimental arm are asked four questions about their experiences using the DST.
- **HIV Prevention Method Continuation:** A self-reported measure of HIV prevention method continuation.
- **HIV Prevention Method Use:** A self-reported measure of HIV prevention method use, including those who reported discontinuing the initial HIV prevention method(s) that were reported post-clinic visit.

7.1.3 *Additional data to be obtained by chart extraction from the medical record at the end of the study*

Data extracted from the medical record will include participants':

- Zip code at the time of the study visit
- Insurance status at the time of the study visit
- PrEP prescription (ever) and date of prescription
- PEP prescription (ever) and date of prescription
- Dates of HIV testing and results
- Hepatitis B and C diagnoses
- Dates of STI testing and results including chlamydia, gonorrhea, syphilis and trichomonas

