Three months after the last participant has been enrolled, a study RA will submit study participants' medical record numbers to FDOH IT, to extract the following information:

- Zip code at the time of the study visit
- Insurance status at the time of the study visit
- PrEP prescription (ever) and date of prescription
- PEP prescription (ever) and date of prescription
- Dates of HIV testing and results
- Hepatitis B and C diagnoses (ever)
- Dates of STI testing and results including chlamydia, gonorrhea, syphilis and trichomonas (within 6 months and ever)

The Duval County DoH Information Technology (IT) Department will be supplied with a list of study ID numbers and medical record numbers. IT will extract relevant outcome variables and create a dataset ONLY with study ID and outcome variables; no PHI will be included in the main dataset. Only this de-identified dataset will be shared among the study team for analysis. These data will be securely transferred to UCSF for analysis, using MoveIt, an encrypted and secure file transfer program that is used by the Florida Department of Health.

The DoH IT department will also extract aggregate data by clinic during the study period of clinic patient demographics (age, race, insurance status), STI diagnoses, HIV diagnoses, and PrEP & PEP prescriptions. In addition, DoH will provide the number of clinic visits per week for the duration of the study, as well as the number of providers at each site and scope of services of each clinic.

This de-identified information will then be stored on secure servers to ensure the privacy of research participants. Information about the above processes is included in the participant's consent form for the main study.

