4. ELIGIBILITY

4.1 Patient eligibility

We are seeking to recruit female participants presenting to two reproductive health clinics in Duval County, Florida (Magnolia and Center for Women and Children).

Inclusion and exclusion criteria are the same at all study sites.

Inclusion Criteria:

- Self-identify as a woman (regardless of pregnancy status)
- Age 18 years old or over
- Not known to be living with HIV (based on self-report)
- English speaking

- Interested in participating in the study

Exclusion criteria:

- Unable to consent
- Currently using PrEP
- Cisgender men
- Unwilling to be contacted in 3 months
- Already participated in the study

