7.2 Sample Size

We plan to recruit up to 384 patient participants total and up to 35 provider participants. Of the 384 patient participants, up to 60 will participate in audio recordings and 40 will participate in an in-depth interview.

Using standard methods, we estimate that a sample of 320 women will provide 80% power in two-sided tests with alpha of 0.05 to detect a between-group difference of 10 percentage points in PrEP uptake, from 5% among controls to 15% in the intervention arm. This estimate is conservative, for two reasons. First, in addition to multiple imputation, which will capture some information from women with missing 3-month outcomes, we will enroll 384 women to protect against a loss to follow-up of up to 20%. Second, because women rather than providers will be randomized, any within-provider clustering of outcomes will increase precision in the proposed mixed models including random effects for provider.

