### 1.2 Study Design and Randomization

The study is a parallel-group Randomized Control Trial with up to 384 participants recruited from family planning sites in Duval County, Florida and randomized 1:1 into two groups (192 in intervention group, 192 in control). Study duration: 3 months.

Treatment: Participants in this arm will receive the HIV prevention DST intervention and will receive the intervention immediately before their provider visit.

Control: Participants in this arm will receive usual care.

Randomization procedures: Randomization will be implemented using randomly permuted blocks of randomly selected size 2 and 4, stratified by clinic and race. All randomization will occur by research staff with the use of a REDCap randomization instrument.

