#### 3.3.1 Primary analysis (H1)

PrEP prescriptions within 3 months of primary study visit will be extracted from participants' electronic medical records (EMRs). Data will be matched to survey data using participant medical record numbers (MRNs). Summary statistics will be presented by treatment group. Differences in PrEP prescriptions between groups will be examined by  $\chi^2$  or Fisher's exact-tests as appropriate. Effect size will be calculated.

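### The primary outcome is named PrEP initiation but counts any in-window charted prescription, and no rule separates first prescriptions from re-prescriptions to earlier or undisclosed users

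*Protocol*

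**What the plan says.** **Question and outcome.** SAP 1.1 (Aim 1a) asks whether women start PrEP within 3 months. Protocol 7.1 says: "The primary outcome will be PrEP initiation within 3 months of the initial visit, as measured by PrEP prescriptions ascertained from chart review". SAP 2.2 treats starting PrEP (hypothesis 2) and still using it at 3 months (hypothesis 11) as different things.

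**What is counted.** SAP 3.3.1 says: "PrEP prescriptions within 3 months of primary study visit will be extracted from participants' electronic medical records (EMRs". SAP 2.1.2.1 defines the variable as the number of participants with a charted prescription and its date, and does not mention the 3-month window. Neither section requires a first or new prescription.

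**Who may enrol.** The PrEP exclusion in protocol 4.1 is "Currently using PrEP". The information card in protocol 3.2.3 and the inclusion list in SAP 1.3 likewise refer only to taking PrEP now. Eligibility is established by spoken questions at screening. Neither document sets a never-used criterion, a look-back period or a chart check before enrolment.

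**What is extracted.** Protocol 3.2.5 and 7.1.3 list "PrEP prescription (ever) and date of prescription". The pull takes place three months after the last enrolment. No rule in either document uses the earlier history.

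**The concern.** A woman who stopped PrEP last month is eligible. So, in practice, is a current user who does not say so. If either receives a prescription in the following 3 months, she counts as an initiation, although she has not started PrEP for the first time. The trial would then report on any PrEP prescription while describing it as initiation.

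If these events occur about equally in both arms, they raise the control rate, pull the risk ratio toward 1 and cost power. At the planned 5%, 192 controls yield fewer than 10 events (192 × 0.05 = 9.6), so a few re-prescriptions are a visible share of the count. With so few events, a choice between first and any prescription made after the data are seen could also change the result.

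The data field adds a practical problem. It asks for a single date, whereas the same list asks for HIV and STI test dates in the plural. If the pull returns the earliest date, an in-window prescription to a former user is hidden. If it returns the latest, a woman enrolled early may show a date after her window has closed.

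**Working it through.** **1. The plan's own figure.** Protocol 7.2 and SAP 1.5 state that "a sample of 320 women will provide 80% power in two-sided tests with alpha of 0.05", for a change "from 5% among controls to 15% in the intervention arm". The pooled two-proportion formula gives

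n = [1.96·√(2·0.10·0.90) + 0.842·√(0.05·0.95 + 0.15·0.85)]² / 0.10² = 140.1, or 141 per arm.

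With the continuity correction, n_cc = (n/4)·[1 + √(1 + 4/(n·0.10))]² = 159.5, or 160 per arm and 320 in total. The planned figure reproduces and is not in dispute.

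**2. Denominator.** The primary outcome comes from the chart through the medical record number and needs no 3-month survey response. SAP 1.2 has women "randomized 1:1 into two groups (192 in intervention group, 192 in control". The check therefore uses 192 per arm.

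**3. Model.** Let f be the share of women with prior PrEP and r their probability of a prescription in the window, equal in both arms. Assume 5% and 15% in the remaining women. Then

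- control rate = 0.05(1 − f) + f·r
- tool rate = 0.15(1 − f) + f·r
- difference = 0.10(1 − f)
- share of control events that are re-prescriptions = f·r / control rate

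The documents give neither f nor r for these clinics, so both are assumptions. Power is exact binomial for the uncorrected two-sided chi-square test at 0.05.

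| f | r | Control | Tool | Ratio | Share of control events | Power, 192 per arm | Power, 160 per arm |
|---|---|---|---|---|---|---|---|
| 0 | – | 5.0% | 15.0% | 3.0 | 0% | 92% | 87% |
| 2% | 25% | 5.4% | 15.2% | 2.8 | 9% | 90% | 84% |
| 2% | 100% | 6.9% | 16.7% | 2.4 | 29% | 86% | 79% |
| 5% | 25% | 6.0% | 15.5% | 2.6 | 21% | 87% | 80% |
| 5% | 50% | 7.25% | 16.75% | 2.3 | 34% | 83% | 76% |
| 5% | 100% | 9.75% | 19.25% | 2.0 | 51% | 76% | 68% |

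The 160 column shows what would apply if chart data were missing for as many women as the plan allows for follow-up loss.

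**4. Leaving out prior users.** At f = 5%, 192 × 0.95 ≈ 182 women per arm remain. The rates return to 5% and 15%, and power is 91%. The smaller sample costs less than the dilution does.

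**5. A bearing figure.** Protocol 1.1 reports about 19,000 ever-prescribed among 180,000 PrEP-eligible women, or 10.6%. That figure is national and restricted to eligible women, whereas this trial enrols regardless of PrEP eligibility. It does not set f for these clinics.

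**The case against.** Four arguments on the other side carry weight.

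- **The planning rates may already include restarts.** Protocol 7.2 describes 5% and 15% as uptake in the two arms and does not confine them to never-prescribed women. If 5% covers any prescription among eligible controls, nothing is lost against the plan. This stands: the power losses above depend on the other reading.
- **The high re-prescription rates are speculative.** Nothing in the documents suggests that half or all of former users restart within 3 months. At one quarter, power with 192 per arm stays at 87% or more for f up to 5%. This stands too, and it limits the size of the point.
- **The tool may prompt genuine restarts.** A disclosed former user has to decide afresh, which is what the tool supports. If 5% are former users who restart at 25% without the tool and 35% with it, the rates are 6.0% and 16.0%, and power is 90% with 192 per arm. Counting restarts as uptake is a legitimate pragmatic choice, and excluding them from the only primary definition would be debatable.
- **Timing is fairly clear in context.** Aim 1a and the description of follow-up imply a prescription after the visit. The missing words in SAP 2.1.2.1 and 3.3.1 are a drafting gap.

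None of this answers the central point. The stated question is initiation, the counted event is any in-window prescription, and the history that would separate the two is to be extracted with no rule for its use.

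A reader might infer that old prescriptions of any date count, because SAP 2.1.2.1 has no window. Protocol 7.1 and SAP 3.3.1 supply the window, so the documents do not support that.

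**Conclusion.** The outcome label and its definition do not match, and the plan should resolve this before the extraction. The consequences are a result described as initiation that partly is not, a risk ratio pulled toward 1, and some loss of power. With 192 per arm the illustrative loss runs from 92% to 90% at the mild end (2% prior users, a quarter re-prescribed) and to 76% at the extreme end (5%, all re-prescribed). Only that last scenario falls below the planned 80%. These figures assume 5% and 15% in women without prior PrEP, complete chart data and no tool effect on re-prescription. The true prior-use share is unknown.

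Two stronger conclusions might be drawn, and the documents support neither. The first is that the comparison is biased in favour of the tool. Prior use precedes randomisation and is balanced in expectation, and a test of any prescription keeps its type I error. The second is that the trial is underpowered. That would need high assumed rates of both prior use and re-prescription, and a reading of the planning rates that the sample size section does not state.

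**What to change.** 1. **Protocol 3.2.5 and 7.1.3:** change the extraction field to all PrEP prescription dates, so that each prescription can be placed before, inside or after the woman's own window.
2. **SAP 2.1.2.1 and 3.3.1:** define the event as a PrEP prescription dated from the study visit through 3 months after it. Keep all randomised women in the intention-to-treat primary analysis.
3. **SAP 3.3.1:** pre-specify an initiation analysis that removes women with a charted PrEP prescription before the visit from both numerator and denominator, and report it beside the primary result. Prior prescription is fixed before randomisation. If it is extracted blind to arm, the restriction preserves the randomised comparison. Protocol 3.2.5 already has the IT department work from study and medical record numbers only.

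The cost is some SAP wording, one changed field in a planned pull and slightly more analysis. No new visit or data source is needed. One limit remains: prescriptions outside the extracted record are still missed, so no charted prescription does not mean never used.

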7.2 Sample Size

We plan to recruit up to 384 patient participants total and up to 35 provider participants. Of the 384 patient participants, up to 60 will participate in audio recordings and 40 will participate in an in-depth interview.

Using standard methods, we estimate that a sample of 320 women will provide 80% power in two-sided tests with alpha of 0.05 to detect a between-group difference of 10 percentage points in PrEP uptake, from 5% among controls to 15% in the intervention arm. This estimate is conservative, for two reasons. First, in addition to multiple imputation, which will capture some information from women with missing 3-month outcomes, we will enroll 384 women to protect against a loss to follow-up of up to 20%. Second, because women rather than providers will be randomized, any within-provider clustering of outcomes will increase precision in the proposed mixed models including random effects for provider.

7.3 Quantitative Data Collection

Data from surveys will be entered into REDCap by participants with the use of a tablet computer, and by research staff in real-time over the phone during follow-up.

After obtaining informed consent, research staff will explain and administer the pre-visit survey, which collects information on HIV prevention knowledge and interest, before the intervention participants use the decision support tool.

After the participant's visit with the provider, they will be asked to complete a post-visit survey about their clinic visit and counseling, risk perception, decision making, sexual history, and their experience with the decision support tool if they are in the intervention arm.

Three months post-visit, research staff will follow-up with participants by phone to administer a short survey and ask participants about their chosen HIV prevention method, and if they initiated PrEP.

Upon completion of the study, research staff will extract data from the medical record pertaining to participants' PrEP prescriptions, history of sexually transmitted infections, zip code, and insurance status.

